# 9.2 Serious Adverse Events

An AE is considered a serious adverse event (SAE) if, in the view of either the Investigator or Sponsor, it results in any of the following outcomes:

- Death
- A life-threatening AE

Note: An AE is considered "life-threatening" if, in the view of either the Investigator or Sponsor, its occurrence places the patient or subject at immediate risk of death. It does not include an AE that, had it occurred in a more severe form, might have caused death.

• Inpatient hospitalization or prolongation of existing hospitalization

Note: The term "inpatient hospitalization" refers to any inpatient admission (even if less than 24 hours). For chronic or long-term inpatients, inpatient admission includes transfer within the hospital to an acute/intensive care inpatient unit. Inpatient hospitalization does not include emergency room visits; outpatient/same day/ambulatory procedures; observation/short stay units; rehabilitation facilities; hospice facilities; nursing homes; or clinical research/phase 1 units.

Note: The term "prolongation of existing hospitalization" refers to any extension of an inpatient hospitalization beyond the stay anticipated or required for the reason for the initial admission as determined by the Investigator or treating physician.

Note: Planned hospital admissions or surgical procedures for an illness or disease that was present before the patient received any study drug are not to be considered SAEs unless the condition deteriorated in an unexpected manner during the trial (e.g., surgery was performed earlier than planned).

• A persistent or significant incapacity or substantial disruption of the ability to conduct normal life functions.

Note: An SAE specifically related to visual threat would be interpreted as any potential impairment or damage to the subject's eyes (e.g., hemorrhage, retinal detachment, central corneal ulcer, or damage to the optic nerve).

• A congenital anomaly/birth defect in an offspring of a study subject.

Important medical events that may not result in death, are life-threatening, or require hospitalization may be considered serious when, based upon appropriate medical judgment, they may jeopardize the patient or subject and may require medical or surgical intervention to prevent one of the outcomes listed in this definition.

SAEs are collected at the time the subject signs the Informed Consent Form until the last follow up visit of the study.

# 9.3 **Procedures for Reporting Adverse Events**

All AEs and their outcomes must be reported to the Sponsor, and the IRB/IEC as required by the IRB/IEC, federal, state, or local regulations and governing health authorities and recorded on the appropriate eCRF.

#### 9.3.1 Reporting a Suspected Unexpected Adverse Reaction

All AEs that are 'suspected' and 'unexpected' are to be reported to the Sponsor and the IRB/IEC as required by the IRB/IEC, federal, state, or local regulations and governing health authorities.

#### 9.3.2 Reporting a Serious Adverse Event

To ensure subject safety, all SAEs, regardless of relationship to the device, must be reported within 24 hours of the Investigator's knowledge. All information relevant to the SAE must be recorded on the appropriate CRFs. The Investigator is obligated to pursue and obtain information requested by the Sponsor in addition to that information reported on the CRF. All subjects experiencing a SAE must be followed up and the outcome reported.

In the event of a SAE, the Investigator must obtain and maintain in his/her files all pertinent medical records, information, and medical judgments from colleagues who assisted in the treatment and follow-up of the subject; provide the Sponsor with a complete case history, which includes a statement as to whether the event was or was not suspected to be related to the use of the study drug; and inform the IRB of the SAE within their guidelines for reporting SAEs.

The SAE form must be completed and submitted to [contact].

# 9.4 Procedures for Unmasking

Not applicable as this is an open label study.

# 9.5 Type and Duration of the Follow-up of Subjects after Adverse Events

The Investigator will follow unresolved AEs to resolution until the subject is lost to follow-up or until the AE is otherwise classified. Resolution means the subject has returned to baseline state of health or the Investigator does not expect any further improvement or worsening of the AE. If the patient is lost to follow-up, the Investigator should make 3 reasonable attempts to contact the patient via telephone, post, or certified mail. All follow-ups will be documented in the subject's source document. Non-serious AEs identified on the last scheduled contact must be recorded on the AE eCRF with the status noted.

New information relating to a previously reported serious adverse event must be submitted. All new information for serious adverse events must be submitted within 24 hours following the investigator's knowledge of new information. The investigator may be asked to provide additional follow-up information, which may include discharge summary or extracts from the medical record.

# **10 STATISTICAL METHODS**

Statistical considerations and methods of analyses for this study are provided below; the accompanying Statistical Analysis Plan (SAP) contains complete details of the planned analyses.

# **10.1 Primary Endpoint**

#### **10.1.1 Primary Endpoint**

• Incidence of Adverse Event

#### **10.2 Analysis Populations**

#### **10.2.1** Safety Population

The safety population will include all enrolled subjects who received at least one Tyrvaya® administered with the nasal guide.

# **10.3** Statistical Analysis

This section briefly outlines the planned analyses. The statistical analysis plan (SAP) describes the methods to be used in detail. If the SAP and the protocol disagree, the details and methods of the SAP will prevail.

The AE data collected from this study will be compared with the historical AE data collected for Tyrvaya® alone from OC-01 (varenicline solution) nasal spray Integrated Summary of Safety (ISS). The data comparison will be presented descriptively without inferential statistics comparison.

#### **10.3.1 General Considerations**

No formal sample size calculation will be made in this pilot study. All data, including demographic and baseline characteristics and endpoint measures, will be summarized descriptively. Continuous variables will be summarized with mean, median, and standard deviation. Categorical variables will be summarized with frequency and percentage.

#### 10.3.2 Safety Analysis

The investigator will promptly review each Adverse Event (AE) for accuracy and completeness, and classify each AE according to its intensity, its relationship to drug or administration procedure, and its seriousness. AEs will be coded using version 22.0 of the MedDRA dictionary. AEs will be monitored throughout the study and documented on the appropriate AE form. AEs will be categorized as ocular and non-ocular events as well as by system organ class (SOC) and preferred term (PT), seriousness, severity, and relation to study medications.

All treatment-emergent adverse events (TEAEs) will be summarized. A TEAE is defined as an AE that is new or worsened in severity compared to the first dose of study drug.

TEAEs will be summarized by subject. In addition, the number of TEAE episodes that occurred during the study will be provided in the overall summary of AE table.

The following presentations of TEAEs will be generated:

- Overall adverse events summary (including any TEAEs, ocular TEAEs, resolved ocular TEAEs, non-ocular TEAEs, ocular TEAEs, non-ocular TEAEs, SAEs, treatment-emergent SAEs, treatment-related treatment emergent SAEs, TEAEs by maximum severity, TEAEs by relationship to study drug, AEs leading to treatment/study discontinuation)
- Serious adverse events (SAE) by SOC and PT;
- All ocular TEAEs by SOC and PT;
- All non-ocular TEAEs by SOC and PT;
- TEAEs leading to treatment discontinuation;
- TEAEs leading to study discontinuation

#### 10.3.3 Interim Analysis

No interim analysis is planned for this study.

# 11 COMPLIANCE WITH GOOD CLINICAL PRACTICES, ETHICAL CONSIDERATIONS, AND ADMINISTRATIVE ISSUES

This study will be conducted in compliance with this protocol, Good Clinical Practices, including the International Conference on Harmonization (ICH) Guidelines, and in general, consistent with the Declaration of Helsinki. In addition, all applicable local, state, and federal requirements relevant to the use of study drugs/devices in the countries involved will be adhered to.

### 11.1 Protection of Human Subjects

#### 11.1.1 Subject Informed Consent

Informed consent/assent must take place before any study specific procedures are initiated. Signed and dated written informed consent must be obtained from each subject and/or from the subject's parent or legal guardian prior to enrollment into the study. If the subject is under the legal age of consent, the consent form must be signed by a legal guardian or as required by state and/or local laws and regulations.

All informed consent/assent forms must be approved for use by the Sponsor and receive approval/favorable opinion from an IRB prior to their use. If the consent form requires revision (e.g., due to a protocol amendment or significant new safety information), it is the Investigator's responsibility to ensure that the amended informed consent is reviewed and approved by Sponsor prior to submission to the governing IRB and that it is read, signed and dated by all subjects subsequently enrolled in the study as well as those currently enrolled in the study.

If informed consent is taken under special circumstances (oral informed consent), then the procedures to be followed must be determined by Sponsor and provided in writing by Sponsor prior to the consent process.

Tyrvaya® Clinical Trial Protocol: OPP-009

#### **11.1.2 Institutional Review Board Approval**

This study is to be conducted in accordance with IRB regulations [U.S. 21 Code of Federal regulations (CFR) Part 56.103]. The Investigator must obtain appropriate IRB approval before initiating the study and re-approval at least annually.

Only an IRB-approved version of the informed consent form will be used.

# 11.2 Ethical Conduct of Study

This study will be conducted in accordance with the ethical principles that originated with the Declaration of Helsinki.

# **11.3 Subject Confidentiality**

All personal study subject data collected and processed for the purposes of this study should be maintained by the Investigator and his/her staff with adequate precautions so as to ensure the confidentiality of the data in accordance with local, state, and federal laws and regulations.

Monitors, auditors and other authorized representatives of the Sponsor, the IRB approving this study, the Food and Drug Administration, the Department of Health and Human Services, other domestic government agencies, and other foreign regulatory agencies will be granted direct access to the study subject's original medical and study records for verification of the data and/or clinical trial procedures. Access to this information will be permitted to the above listed individuals to the extent permitted by law.

A report of the results of this study may be published or sent to the appropriate health authorities in any country in which the study drug may ultimately be marketed, but the subject's identity will not be disclosed in these documents.

# **11.4 Documentation**

Source documents may include a subject's medical records, hospital charts, clinic charts, the Investigator's study subject files, as well as the results of diagnostic tests such as photographs, X-rays, laboratory tests, and electrocardiograms. The Investigator's copy of the CRFs serves as the Investigator's record of a subject's study-related data.

#### **11.4.1 Retention of Documentation**

All study related correspondence, subject records, consent forms, record of the distribution and use of all study drug and copies of CRFs should be maintained on file for at least two years after the last approval of a marketing application in an ICH region and until there are no pending or contemplated marketing applications in an ICH region; or until at least two years have elapsed since the formal discontinuation of clinical development of the study drug. These documents will be retained for a longer period if required by the applicable regulatory requirements or by an agreement with the Sponsor. It is the responsibility of the Sponsor to inform the Investigator/institution as to when these documents no longer need to be retained.

If the responsible Investigator retires, relocates, or for other reasons withdraws from the responsibility of keeping study records, custody must be transferred to a person who will accept the responsibility. The Sponsor must be notified in writing of the name and address of the new custodian.

# 11.5 Labeling, Packaging, Storage, Accountability, and Return or Disposal

#### 11.5.1 Labeling and Packaging

Commercially available Tyrvaya® will be utilized in this study. Please refer to the Tyrvaya® package insert for additional information.

The nasal guide will be provided individually wrapped and sealed in plastic storage bag. Please refer to the nasal guide package insert for additional information.

#### **11.5.2** Storage of Nasal Guide

The nasal guide can be stored ambient temperature at 20°C to 25°C (68°F to 77°F).

#### 11.5.3 Accountability of Nasal Guide

The nasal guide is only prescribed by the principal Investigator or his/her named sub investigator(s) and is to only be used in accordance with this protocol. The nasal guide must only be distributed to subjects properly qualified under this protocol. The Investigator must keep an accurate accounting of the nasal guide by maintaining a detailed inventory. This includes the amount o received by the site, amount dispensed to subjects, amount returned to the site by the subjects, and the amount returned to the Sponsor upon the completion of the study.

#### 11.5.4 Return or Disposal of Nasal Guide

You may be requested to destroy the nasal guides at the end of the study. If site regulations do not permit destruction, the nasal guides will be returned to the Sponsor or their designee for destruction.

# **11.6 Recording of Data on Source Documents and Electronic Case Reports Forms**

All subject data will be captured in the subject source documents which will be transcribed in the eCRFs. The Investigator is responsible for ensuring that study data is completely and accurately recorded on each subject's eCRF, source documents, and all study-related materials. All study data should also be attributable, legible, contemporaneous, and original. A recorded datum should only be corrected in a manner that does not obliterate, destroy, or render illegible the previous entry (e.g., by drawing a single line through the incorrect entry and writing the revision next to the corrected data). An individual who has corrected a data entry should make clear who made the correction and when, by adding to the correction his/her initials as well as the date of the correction.

Data entry of all enrolled and randomized subjects will use software that conforms to 21 CFR Part 11 requirements and will be performed only by staff who have been trained on the system and have access to the system. Minimal data will be entered for screen failure subjects. An audit trail will be maintained within the electronic system to capture all changes made within the eCRF database. After the end of the study and database lock, electronic copies of all applicable subjects' eCRFs will be provided to each Investigator Site to be maintained on file by the Investigator.

# **11.7 Handling of Biological Specimens**

Not applicable.

# **12 REFERENCES**

# **13. APPENDICES**

# **Appendix 1: Nasal Guide Instructions for Use**

# Nasal Guide

**Intended Purpose:** Nasal Guide is an optional accessory that helps you administer TYRVAYA® (varenicline solution) Nasal Spray by pointing the spray tip in the correct direction inside the nose and ensuring the tip doesn't go too far into the nose. For use only with TYRVAYA, as prescribed by your doctor.

Instructions for Use: Before using Nasal Guide, read these instructions and the Instructions for Use supplied with TYRVAYA. Do not discard these instructions. If you have questions, please ask your doctor or your pharmacist. Keep accessory out of the reach of children. Prepare TYRVAYA for use including priming steps per the Instructions for Use.

Attach Nasal Guide to TYRVAYA.

- Remove the blue cap from the Tyrvaya nasal applicator.
- Ensure the clip is on prior to attaching the Nasal Guide.
- Slide Nasal Guide down over the tip of the nasal applicator to sit flat against the base of the nasal applicator.
- Remove the clip.

2

Position TYRVAYA correctly.

- When ready to spray TYRVAYA into your nostril, point the arrow on Nasal Guide towards the ear on the same side as your nostril.
- Insert TYRVAYA into the nostril until Nasal Guide touches the bottom of the nose. Administer TYRVAYA per the Instructions for Use.

3

Remove and store Nasal Guide.

- Slide Nasal Guide up from the nasal applicator.
- Wipe Nasal Guide with a clean tissue.
- Store Nasal Guide in its bag until the next use.
- Wipe the TYRVAYA nasal applicator with a clean tissue. Replace the clip and the cap as per the TYRVAYA Instructions for Use.
- The Nasal Guide can be cleaned weekly by soaking for 15 minutes in a mild solution of liquid dish detergent and lukewarm water. Agitate gently. Rinse with clean water and dry with a clean tissue. DO NOT PLACE IN DISHWASHER.

Remove Nasal Guide

© 2022 Oyster Point Pharma, Inc.

Nasal Guide and TYRVAYA® are trademarks of Oyster Point Pharma, Inc. in the United States and certain jurisdictions. All rights reserved.

Manufactured for and distributed by: Oyster Point Pharma, Inc., [name]. [name].

OYSTER © 2022 Oyster Point Pharma, Inc. Oyster Point®, the Oyster Point logo, Tyrvaya®, and the Tyrvaya logo are trademarks of Oyster Point Pharma, Inc. in the United States and certain jurisdictions. All rights reserved.

8.10 Safety Analysis	
Appendix 1 Schedule of Visits and Measurements	

1 Synopsis

Protocol Title:	A Phase 4, Single-Center, Open-Label Study Evaluating the Safety of the Nasal Guide Utilized During Administration with Tyrvaya®
Protocol Number:	OPP-009
Investigational Product:	Nasal guide
Study Objective:	To determine the safety of the nasal guide when utilized to aid in the administration of Tyrvaya® (varenicline solution 0.03 mg) Nasal Spray
Treatment Assignment	30 subjects will be provided the nasal guide to utilize with Tyrvaya® administration.
Sample Size and Power	
Randomization and Stratification	Not applicable
Study Endpoints	Primary endpoints Incidence of adverse events
Statistical Analysis for Primary Endpoint	The AE data collected from this study will be summarized with frequency and percentage. The profile of the adverse events will be made by comparing the results from this study with the external historical AE data collected for Tyrvaya® alone from OC-01 (varenicline solution) nasal spray Integrated Summary of Safety (ISS). The data comparison will be made without inferential statistics.
Analysis Population	

Abbreviations

AE	adverse event
BID	two times a day
FDA	Food and Drug Administration
HIPAA	Health Information Portability and Accountability Act
ICH	International Conference on Harmonization
MedDRA	medical dictionary for regulatory activities
mg	Milligram
SAE	serious adverse event
SAE SAP	serious adverse event Statistical Analysis Plan
2112	
SAP	Statistical Analysis Plan
SAP SD	Statistical Analysis Plan Standard deviation

2 Introduction

This statistical analysis plan (SAP), which is based on the original protocol of the study protocol dated May 02, 2023, defines the methods, and analyses that Oyster Point Pharma, Inc. (henceforth, Oyster Point) plans to use to analyze and summize the data from Protocol OPP-009. This SAP complies with guidance promulgated by the International Conference on Harmonization (ICH) and the US Food and Drug Administration (FDA). If the protocol is subsequently amended, this SAP may be amended as well. Should the SAP and the protocol be inconsistent with respect to the planned analyses, the language of the SAP prevails.

3 Study objective

The objective of this study is to determine the safety of the nasal guide during administration of Tyrvaya® (varenicline solution 0.03 mg) Nasal Spray.

4 Study Design

This is a single center, open-label study to evaluate the safety of the nasal guide during administration of Tyrvaya® (varenicline solution 0.03 mg) Nasal Spray. This study will consist of two visits over 7 days.

At Visits 1 and 2, the subjects will attach the nasal guide and administer one spray of Tyrvaya® (varenicline solution 0.03 mg) nasal spray in each nostril. In between study visits, subjects will administer one spray of the nasal spray in each nostril twice daily (BID) approximately 12 hours apart at home using the nasal guide.

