# **3** CLINICAL HYPOTHESIS

This study is testing the hypothesis that the use of the nasal guide with Tyrvaya® does not introduce any additional safety concerns as compared to the safety of Tyrvaya® alone.

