#### 8.9 Monitoring and Quality Assurance

9 SAFETY DEFINITIONS, MONITORING AND REPORTING

#### 9.1 Adverse Events

An adverse event (AE) is defined as any untoward medical occurrence associated with the use of a drug or device in humans, whether the event is considered drug or device related or not. An AE can therefore be any unfavorable and unintended sign (e.g., an abnormal laboratory finding), symptom, or disease occurring after the subject started dosing with the device, without any judgment about causality. Any pre-existing medical condition that worsens after administration of the nasal guide will also be considered a new AE.

AE collection will start following the first administration of Tyrvaya® utilizing the nasal guide until the last follow up visit of the study.

Documentation regarding the AE should be made as to the nature, date of onset, end date, severity, relationship to study drug, action(s) taken, seriousness, and outcome of any sign or symptom observed by the Investigator or reported by the subject upon indirect questioning.

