5.1 Primary Endpoint

The primary endpoint is the incidence of adverse events. The primary endpoint will be summarized based on the safety population.

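### The plan sets 7-day adverse event frequencies against ISS frequencies without aligning the observation windows, so the frequency comparison may lean towards the guide

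*SAP*

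**What the plan says.** - **Hypothesis.** Protocol section 3 says that use of the guide "does not introduce any additional safety concerns as compared to the safety of Tyrvaya" alone. The study has one arm.
- **Comparison.** Protocol 10.3: "The AE data collected from this study will be compared with the historical AE data collected for Tyrvaya" alone, with the ISS as source. The primary-endpoint row of the SAP section 1 synopsis repeats this: "The profile of the adverse events will be made by comparing the results from this study with the external historical AE data". Both documents rule out inferential statistics.
- **Measure.** SAP 5.1: "The primary endpoint is the incidence of adverse events". The synopsis adds: "The AE data collected from this study will be summarized with frequency and percentage".
- **Window in this study.** SAP section 4: "This study will consist of two visits over 7 days". Protocol 9.1: "AE collection will start following the first administration of Tyrvaya" with the guide, and collection runs to the last follow-up visit, which Protocol 8.3.1 places on Day 7. Protocol 9.5 follows unresolved events further but does not extend the collection of new ones.
- **Window in the ISS.** Not given in either document.
- **Alignment.** None of the 12 presentations listed in SAP 8.10.1 sets this study beside the ISS. SAP 8.9 summarises exposure in this study only. SAP 8.3 defines a Dosing Day but does not apply it to the ISS.
- **Sample size.** 30 subjects. Protocol 10.3.1: "No formal sample size calculation will be made in this pilot study".

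**The concern.** The percentage of subjects with at least one event can only stay level or rise as follow-up lengthens. A 7-day percentage placed beside one from a longer period is not like for like, even when the underlying risk is identical. The longer-observed source shows the higher figure, and here that source could be the comparator. The comparison would then lean towards the conclusion that the protocol hopes to reach.

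At stake is how a reader interprets two columns of percentages. Since the plan has no test and no decision threshold, the presentation is the only safeguard against misreading them.

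**Working it through.** The plan states no figure to reproduce: it gives no ISS incidence, ISS duration, margin or power. The check therefore shows how large a window effect could be under stated assumptions.

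**Inputs from the documents:** a window of 7 days and n = 30.

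**Assumed inputs:** *p*, the ISS percentage of subjects with at least one event over full ISS follow-up; and *s*, the share of those subjects whose first event falls in days 1–7.

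**Step 1: the shift.** The matched 7-day ISS incidence is *s* × *p*. The excess of the crude ISS figure over it is (1 − *s*) × *p*. With *p* = 20%:

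| *s* | Matched ISS figure | Shift (points) | Shift × 30 subjects |
|---|---|---|---|
| 100% | 1.00 × 20% = 20% | 0 | 0 |
| 75% | 0.75 × 20% = 15% | 5 | 1.5 |
| 50% | 0.50 × 20% = 10% | 10 | 3.0 |

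**Step 2: range over *p*.** At *s* = 100% the shift is zero for every *p*.

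| *p* | Shift at *s* = 75% (points) | Shift at *s* = 50% (points) |
|---|---|---|
| 5% | 1.25 | 2.5 |
| 20% | 5 | 10 |
| 50% | 12.5 | 25 |
| 80% | 20 | 40 |

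**Step 3: a different onset assumption.** If first events arrive at a constant hazard over an ISS follow-up of *T* days, the 7-day figure is 1 − (1 − *p*)^(7/*T*). With *p* = 20% this is 20.0% for *T* = 7, 10.6% for *T* = 14, 5.4% for *T* = 28 and 1.8% for *T* = 84. The shifts are 0, 9.4, 14.6 and 18.2 points. The values of *T* are also assumptions. Early-clustered onset gives smaller shifts, as in step 1.

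**Step 4: precision.** If 3 of 30 subjects had an event (10%), the exact (Clopper-Pearson) 95% interval would be 2.1% to 26.5%. It contains 10%, 15% and 20%, every matched figure in step 1. Matching the windows removes a directional shift; it does not make 30 subjects precise.

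**The case against.** **No mismatch is shown.** ISS duration, incidence and onset timing are all absent, and the range in step 2 includes zero. This stands. A reader might infer that the planned comparison is biased towards the guide, or that it would hide a harm. The documents support neither: the first needs ISS facts that they do not give, and the second needs a decision rule that the plan does not have.

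**The comparison is descriptive, in a pilot of 30.** True, so no error rate or power is affected. Imprecision does not cancel a directional shift, however.

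**Frequency may not be part of the comparison.** The synopsis sentence on percentages concerns this study's data, and the ISS sentence speaks of a profile. Reading frequency into the comparison is an inference, but a reasonable one: both sentences sit in the primary-endpoint row, and that endpoint is incidence. A reader might also infer from SAP 8.10.1 that the ISS comparison was dropped. That does not follow, since its list covers this study's treatment-emergent events and the synopsis still plans the comparison.

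**A Day 1–7 cut could do harm.** If the cut ISS replaced the full ISS, a known Tyrvaya event with later onset could look new to the guide. This stands and shapes the fix. Recognition of new kinds of event is less affected by the window than frequency is, but it is not immune. Late-onset kinds can be missed in 7 days, and longer ISS follow-up can list more terms.

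**Day 1 may not mean the same thing.** The readable text does not settle whether subjects had already used Tyrvaya: there is no washout, no exclusion criteria apply, and two inclusion items are not readable. This stands as a caveat.

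**Some fields are blank or cut.** They are not counted as omissions. The sections where an alignment rule would belong (SAP synopsis analysis row, 8.1, 8.9 and 8.10.1; Protocol 10.3) are readable in substance and contain none.

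**Conclusion.** The concern holds in conditional form. The one analysis that addresses the comparative hypothesis sets frequencies from a 7-day window against ISS data, with no onset restriction or exposure adjustment in the readable plan. If ISS follow-up exceeds 7 days and some first events come after day 7, the crude ISS percentages are inflated relative to this study by (1 − *s*) × *p*, which favours the guide. That is 5 or 10 points at an assumed 20% incidence with 75% or 50% early onset. It is zero if all first events fall in days 1–7.

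Confidence is medium: the absence of a rule is documented, while the size rests wholly on ISS figures outside the documents. This is a cheap improvement to the analysis plan and does not invalidate the study.

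**What to change.** Add one descriptive table to SAP 8.10.1, with any-event, SOC and PT rows, all in one MedDRA version (the SAP specifies 26.0), and three columns:

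1. All treatment-emergent events of this study, with none dropped.
2. ISS treatment-emergent events on Tyrvaya alone with onset on Dosing Days 1–7, as the reference for frequency. SAP 8.3 already supplies the day count, reading the first dosing date as Day 1.
3. The full, uncut ISS percentages with their follow-up duration, as the reference for kinds of event.

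Footnote whether study subjects had used Tyrvaya before Day 1, because prior use would make the alignment inexact.

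If subject-level ISS onset dates are not available, print the ISS follow-up duration beside the ISS percentages and this study's exposure from SAP 8.9. State that the frequency comparison is not window-matched.

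**Cost.** The fallback needs one SAP sentence and a footnote. The full table needs some ISS reprogramming and possibly recoding, and depends on data access that the documents do not describe. Neither changes data collection. The sponsor should expect the matched historical percentages to be the same or lower, and so less favourable to the guide.
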